4. SELECTION AND ENROLLMENT OF SUBJECTS

4.1. Inclusion Criteria

1. Age 18-80
2. Diagnosis of confirmed cryptogenic symptomatic distal symmetric peripheral polyneuropathy based on the Toronto consensus criteria for probable neuropathy (the presence of **unequivocal** signs and symptoms of neuropathy)⁴⁵.
3. Evidence of symptomatic neuropathy based on a screening visit NQOL-DN score of >9
4. Metabolic syndrome based on modified ATP III criteria, with a BMI ≥ 25 kg/m² ⁴⁶. Specific criteria require 3 of the following 6 to be present at the screening visit.
 - Waist circumference >102 cm for men, >88 cm for women
 - Serum triglycerides of ≥ 150 mg/dl
 - HDL < 40 mg/dl for men, < 50 mg/dl for women
 - Those with either a normal HDL or TRG who are taking a lipid lowering medication for this purpose.
 - Blood pressure $\geq 130/85$ mm Hg or use of anti-hypertension drug
 - Prediabetes based on American Diabetes Association (ADA) criteria at screening based on any one or more of the following: fasting plasma glucose - 100 mg/dL to 125 mg/dL (5.6 mmol/L to 6.9 mmol/L),
2-hour glucose tolerance test - 140 mg/dL to 199 mg/dL (7.8 mmol/L to 11.0

mmol/L), or hemoglobin A1c between 5.7% and 6.4%.

5. No current or prior history of therapy with topiramate.
6. If female of child-bearing potential (i.e., not surgically sterile or post-menopausal defined as age > 51 years without menses for ≥ 2 years), negative serum pregnancy test at screening and negative urine pregnancy test at baseline visit.
7. Women of child-bearing potential or men with sexual partners of childbearing potential be willing to use an acceptable method of birth control for the duration of the study and for 12 weeks following completion of study drug therapy. Acceptable methods of birth control include abstinence, oral contraceptives, the contraceptive patch, intra-uterine device, the contraceptive ring, and or barrier contraception such as condoms with spermicide.

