4.4.5. Randomization/Treatment Assignment

Randomization to study treatment (either topiramate or matching over-encapsulated placebo) will occur using an interactive web response system (IWRS). Online randomization will follow confirmation of eligibility and completion of all required baseline procedures. Randomization codes will be constructed using random permuted blocks to assure balanced randomization over time with stratification by BMI. BMI of 30.0 will serve as stratification cutoffs reflecting anticipated median values.

Following randomization, subjects will be given a supply of study drug with instructions to take the study drug twice daily using a 2-week dose escalation schedule. Subjects will titrate to two 25mg tablets twice daily, or the maximally tolerated dose.

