5.4.1. Prohibited Medications/Interventions

The following medications/interventions are exclusionary:

- Therapeutic anticoagulations including coumadin or oral factor X or thrombin inhibitor therapy
- Topical capsaicin
- Oral prednisone
- Carbonic anhydrase inhibitor (such as acetazolamide)
- Weight loss medications
- Neuropathic pain agents beyond first line agents
- Scheduled opiates, or as needed opiate medications more than three times weekly
- Intrathecal pain pump or spinal cord stimulator
- Current or prior history of topiramate therapy

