5.5. Subject Compliance

At each study visit, the site Investigator and/or Study Coordinator will assess the subject's compliance with the study requirements. This will include checks for protocol compliance, including use of study drug in order to assess the reliability of subject-generated data. Subjects who fail to comply with study requirements may be withdrawn from the study.

A serum topiramate level will be measured at baseline and weeks 32, 64, and 96 or ET to assess for compliance or potential crossover (e.g. a participant randomized to placebo taking off study prescription topiramate).

Participants will be asked to hold their morning dose of study medication until after the blood draw at weeks 32, 64, 96/ET. The date and time of last dose of study drug will be recorded. If the participant does not hold the prior dose, the topiramate level should still be obtained. These data will not be shared with the study team until after the study has closed.

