6.4. Visit 02 Baseline (Day 0)

Participants who continue to meet all inclusion/exclusion criteria after screening will present to the clinic for the baseline visit. The baseline visit will be performed within 30 days of the screening visit. However, the investigator will review, date and initial the screening laboratory assessments to confirm participant eligibility for study participation prior to the baseline visit procedures. Therefore, adequate time must be provided for the laboratory results to be received from the central laboratory. The investigator or designee will again review the study inclusion/exclusion criteria and participant medical history, confirming that the participant meets criteria for study participation before randomization.

The following procedures will be performed at the baseline visit (this visit may take about 4 hours):

- Review Inclusion/Exclusion criteria.
- Obtain a medical, family, and neurological history to assess for possible exclusionary conditions. Medical histories should include baseline symptoms, ongoing illnesses, other chronic conditions, surgical history, review of currently used medications, as well as any other important information that may affect the conduct of the study. See section 7.1.3.

- Review concomitant medications, including all nutritional, herbal and alternative therapies. See section 7.1.4.
- Review interval medical history.
- Review adverse events.
- Perform vital sign measurements: blood pressure (systolic and diastolic), heart rate (beats/minute), and body temperature (°C). See section 7.1.6.
- Record weight (kg) and Body Mass Index (BMI).
- Perform an abbreviated Physical Examination, including visual field and fall risk assessment.
- Perform Functional and Mobility testing (6MWT, TUG, ABC Scale). See section 7.1.11.
- Perform nerve conduction studies. See section 7.1.13.
- Perform distal thigh skin biopsy. See section 7.1.14.
- Collect blood samples for routine hematology panel blood, basic metabolic panel, topiramate level and DNA analysis (OPTIONAL). See section 7.1.12.
- Collect urine for a urine pregnancy test (pregnancy test for women of child-bearing potential only).
- For women of childbearing potential and sexually active males, review acceptable birth control methods that must be used during the study.
- Perform subject randomization via interactive voice response system (IVRS) and/or interactive web response system (IWRS). See section 4.4.5.
- Dispense study drug.

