7.1.12. Laboratory Evaluations

Clinical laboratory evaluations for the study will be analyzed by the NeuroNEXT central laboratory at the University of Rochester. Refer to the *University of Rochester Medical Center Lab Manual* for sample handling and processing requirements.

The following laboratory assessments will be performed throughout the study:

- Safety monitoring laboratory tests:
 - Complete Blood Count (CBC)
 - Basic Metabolic Panel (BMP) including Sodium, Potassium, Chloride, Carbon Dioxide, Urea Nitrogen, Glucose, Creatinine, Calcium, and Anion Gap (optional).
 - Hematology Panel
 - Serum Pregnancy Test (for women of child-bearing potential only)
 - Urine Pregnancy Test (for women of child-bearing potential only)

NN108 Topiramate as a Disease Modifying Therapy for CSPN

Version 8.0

Version date 8/8/2018

- Baseline metabolic monitoring laboratory tests. These are intended to assess the metabolic effects of therapy and to confirm the presence of metabolic syndrome for inclusion criteria and evaluation throughout the study:
 - Fasting Insulin
 - Fasting Lipid Panel including Cholesterol, Triglycerides, Calculated LDL Cholesterol, and HDL Cholesterol.
 - 2-hour Oral Glucose Tolerance Test (OGTT) using a 75g anhydrous dextrose oral load with the first blood draw (pre-dextrose) prior to 10 am. The second draw will be 2 hours post dextrose. The subject will remain sedentary during the following two hours.
 - HgbA1C
- Laboratory evaluation for additional causes for neuropathy:
 - Vitamin B12
 - Serum Immunofixation
- Serum topiramate levels will be measured at Baseline and weeks 32, 64, and 96 (or ET) in order to assess for compliance and treatment crossover.

Participants will be asked to hold their morning dose of study medication until after the blood draw at weeks 32, 64, 96/ET. The date and time of last dose of study drug will be recorded. If the participant does not hold the prior dose, the topiramate level should still be obtained.

Topiramate laboratory kits, shipping materials, and requisitions will be provided by Utah. The sample will be obtained in a red collection tube with serum separated by centrifuge within 2 hours. Serum will be placed in the transport vial and refrigerated prior to being placed on a cold pack for shipment. The sample will be returned to Utah with the skin biopsy sample. Samples should be received by Utah cool (not frozen). The results will be made available to the DSMB.

- DNA sample (OPTIONAL)

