10.2. Data Monitoring

All aspects of the study will be monitored by qualified individuals designated by the sponsor. Monitoring will be conducted according to Good Clinical Practice and applicable government regulations. The investigator agrees to allow monitors access to the clinical supplies, dispensing and storage areas, and to the clinical files of the study subjects, and, if requested, agrees to assist the monitors.

Safety monitoring will include careful assessment and appropriate reporting of adverse events. Medical monitoring will include contemporaneous assessment of serious adverse events.

The monitoring of subject safety and data quality will follow the NINDS Guidelines for Data and Safety Monitoring in Clinical Trials. A Data and Safety Monitoring Board (DSMB) appointed by the NIH/NINDS will meet at 24-week intervals (or as determined by the NINDS) to review partially unblinded study data provided by the study statistician. This committee will monitor rates of adverse events and endpoints in the trial and will monitor the performance of the trial. The frequency and format of DSMB meetings, reports, and guidelines for interim analysis will be agreed upon prior to study subject enrollment.

The Protocol PI will appoint an Independent Medical Monitor (IMM) to review all adverse events, in a blinded fashion, on a periodic basis. In addition, the IMM will review all events that meet the regulatory definition of a Serious Adverse Event, upon receipt of notification via the Electronic Data Capture (EDC) system.

An adverse event (AE) is any unfavorable and unintended sign (including a clinically significant abnormal laboratory finding, for example), symptom, or disease temporally associated with a study, use of a drug product or device whether or not considered related to the drug product or device. The FDA, Office of Human Research Protection (OHRP), and NeuroNEXT CIRB requirements for reporting AEs will be followed. Subjects will be monitored for AEs from the time they sign consent until 30 days following permanent discontinuation of study drug. Adverse events during the screening phase (from the time the subject signs consent until they are randomized) shall only include events related to study procedures, i.e. infection of skin biopsy site.

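### The baseline topiramate level cannot reveal the arm, yet section 5.5 appears to withhold it from sites and study team until closure, leaving undisclosed current use visible only to the DSMB

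*Combined protocol and SAP*

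**What the plan says.** Topiramate exposure is ruled out twice. Inclusion criterion 5 in section 4.1 requires "No current or prior history of therapy with topiramate", and section 5.4.1 lists "Current or prior history of topiramate therapy" as exclusionary.

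Section 5.5 sets out the assay: "A serum topiramate level will be measured at baseline and weeks 32, 64, and 96 or ET to assess for compliance or potential crossover". After a passage on holding the morning dose at the later visits, the subsection ends: "These data will not be shared with the study team until after the study has closed".

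Section 7.1.12 repeats the sampling times and the purpose, sends the sample to Utah with the skin biopsy, and adds: "The results will be made available to the DSMB". It gives no timing for this and no action to follow. The same section has the investigator or a designee review and sign off laboratory evaluations, and makes no exception for topiramate levels.

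On sequence, section 6.4 places the baseline draw at Visit 02, Day 0. Section 4.4.5 states: "Online randomization will follow confirmation of eligibility and completion of all required baseline procedures". Under section 5.3.2, dosing starts in the evening.

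Section 10.2 plans DSMB meetings every 24 weeks unless NINDS decides otherwise. The board's listed tasks are adverse events, endpoints and trial performance.

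**The concern.** An embargo on drug levels protects the blind, because after randomisation a measurable level identifies the active arm. At baseline nobody has taken study drug, so that reason does not apply. The one thing a detectable baseline level indicates is that the participant is already taking a drug that makes them ineligible.

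The population makes this conceivable. The trial enrols people with metabolic syndrome and a BMI of at least 25, section 2.4 lists a topiramate combination among the marketed weight-loss drugs, and section 5.5 itself foresees off-study prescription use.

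A participant on undisclosed topiramate in the active arm would take study drug on top of an existing prescription. In the placebo arm, the control would be exposed from the first day. The site, which handles eligibility and day-to-day safety, would not see the result that shows this.

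**Working it through.** The check is mainly a comparison of sections, with one calculation for scale.

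**1. Can the baseline level reveal the arm?** The draw is a baseline procedure (6.4), randomisation follows those procedures (4.4.5), and the first dose is taken that evening (5.3.2). The level is therefore pre-dose and carries no information about assignment.

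**2. Does the embargo cover it?** The subsection describes one series, baseline included, and the embargo sentence exempts nothing. However, the sentences just before it concern only weeks 32, 64 and 96/ET. If the embargo covers the whole series, the baseline result is withheld. If it covers only the later samples, the protocol names no recipient of the baseline result except the DSMB. Both readings need the text clarified.

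**3. Is there another route to the site?** Section 11.3.3 describes results going back to sites only for safety laboratory tests run at the Rochester central laboratory. Topiramate samples go to Utah (7.1.12), and no return to sites is described.

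**4. How long would the result be withheld?** Section 2.2 expects recruitment over 48 weeks and the last visit about 144 weeks after the first enrolment. If closure is no earlier than that last visit, the wait is about 144 weeks for the first participant and 144 − 48 = 96 weeks for the last. In every case the planned treatment period is over. The DSMB could see a result within about 24 weeks at the planned meeting interval.

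**5. Would release prevent randomisation?** No. The draw is at the randomisation visit and the assay is off site.

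**6. Effect on power.** The plan's NQOL-DN calculation (section 10, item e) uses an SD of change of 16.4, correlation 0.60, 125 randomised, 12% loss and a difference of 7.9 points at two-sided 0.05.

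- Follow-up SD: 16.4/√(2 × (1 − 0.60)) = 18.34
- Residual SD after baseline adjustment: 18.34 × √(1 − 0.60²) = 14.67
- Per arm: 125 × 0.88/2 = 55
- Standard error: 14.67 × √(2/55) = 2.80
- Power: Φ(7.9/2.80 − 1.96) = 80.6%. The difference detectable at 80% power is 7.84, against the stated 7.9, so the plan's figure reproduces.

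Let *f* be the assumed share of participants who contribute no treatment contrast, so the difference becomes 7.9 × (1 − *f*). The documents give no value for *f*.

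| *f* (assumed) | Participants of 125 | Power |
|---|---|---|
| 0 | 0 | 80.6% |
| 1% | 1.25 | 79.8% |
| 2% | 2.5 | 79.0% |
| 5% | 6.25 | 76.5% |

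Equivalently, one exposed control in a placebo arm of about 62 dilutes the contrast by 1/62 = 1.6%.

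**The case against.** The strongest reply is that giving drug levels to an independent board and not to the blinded team is a recognised design choice, and that the topiramate exclusion has its own checks. Medical history, medication review and the eligibility check are done at both screening and baseline (6.2, 6.4), and concomitant medications are reviewed at every later visit. The assay's stated purpose is compliance and crossover, not eligibility. The DSMB's meeting frequency and reports are to be agreed before enrolment and could cover this. Most of that stands, and it limits the point to undisclosed current use.

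A reader might infer more than the documents support:

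- *That the embargo causes ineligible people to be randomised.* It does not. With a same-day draw and off-site assay, the result would come too late even if released at once.
- *That such use goes undetected.* Section 7.1.12 gives the results to the DSMB. What is missing is a rule for what the board does with a positive baseline level or how the site learns of it.
- *That the assay verifies criterion 5.* A serum level reflects recent use and cannot test the prior-history half.
- *That the contrast is seriously weakened.* No rate of undisclosed use is given, and the effect on power is small for any plausible small number of cases.

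The conflict with the investigator sign-off rule should not be pressed too far either. Read literally, that rule would also cover the later levels, which must stay masked. It shows that the two provisions need reconciling, not that the embargo was a mistake.

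**Conclusion.** The point holds in a limited form. The blinding rationale does not extend to the baseline sample, and no section links a detectable baseline level to the topiramate exclusion, to deviation reporting or to notifying the site. The DSMB is the only named early recipient.

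This rests on two readings: that the embargo covers the full series, and that the undefined study team includes the sites. If the first is wrong, the defect is silence about the baseline result instead of withholding, and the same clarification is needed.

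The importance is low. The benefit is earlier recognition of an ineligible participant who may be taking study drug together with a prescription. The statistical consequence is negligible unless undisclosed use is far commoner than there is any reason in the documents to assume.

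**What to change.** In sections 5.5 and 7.1.12:

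- Limit the embargo to the week 32, 64 and 96/ET samples.
- State that the baseline result goes to the site and the Independent Medical Monitor when available.
- Record a detectable baseline level as an inclusion/exclusion deviation under section 7.1.2, which already classes these as major.
- State that the participant stays in the intent-to-treat analysis.
- Reconcile the embargo, the DSMB release and the investigator sign-off rule on who sees which level and when.

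Any treatment decision stays with the investigator under the existing rules.

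This gives an early catch after randomisation, not an entry gate. It needs no new sample or visit and carries no unblinding risk, because the sample is pre-dose. The cost is a few sentences of protocol text and a modest amount of laboratory release work. How early the catch comes depends on whether the laboratory assays samples on receipt or in batches, which the documents do not state and the sponsor should confirm.

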6. STUDY PROCEDURES

6.1. Schedule of Assessments

Recruitment will take place over 48 weeks. The study will consist of screening and baseline visits, safety and monitoring visits every 16 weeks, evaluation visits at 32, 64, and 96 weeks, and a final safety assessment visit or telephone assessment following termination of study drug. A Schedule of Assessments is provided in Appendix A.

6.2. Visit 01 Screening (Day -30 to 0)

Up to 30 days will be allotted to complete the screening assessments. Prior to any involvement in study related activities, the participant must sign and date a central Institutional Review Board (IRB) approved written informed consent form (ICF). A copy of the signed and dated ICF must be given to the participant. Screening visit procedures may be performed over two consecutive days if scheduling constraints prohibit the completion of all study procedures in a single day. If screening procedures are completed over two days, the baseline visit will occur within 30 days of the last screening procedure completion.

The following procedures will be performed at the screening visit (this visit may take approximately 3 hours):

- Obtain written informed consent from participant.
- Review inclusion/exclusion criteria.
- Obtain a medical, family, and neurological history to assess for possible exclusionary conditions. Medical histories should include baseline symptoms, ongoing illnesses, other chronic conditions, surgical history, review of currently used medications, as well as any other important information that may affect the conduct of the study. See section 7.1.3.

- Review concomitant medications, including all nutritional, herbal and alternative therapies. See section 7.1.4.
- Administer the *Norfolk Quality of Life-Diabetic Neuropathy scale* (NQOL-DN). See section 7.1.19.
- Perform a general medical and detailed neuromuscular physical examination. See section 7.1.5.
- Perform vital sign measurements: blood pressure (systolic and diastolic), heart rate (beats/minute), and body temperature (°C). See section 7.1.6.
- Record weight (kg), height (cm) and Body Mass Index (BMI).
- Record waist circumference (cm). See section 7.1.7.
- Perform a resting 12-Lead ECG. See section 7.1.8.
- Collect blood samples for CBC, fasting basic metabolic panel, fasting insulin, fasting lipid panel, two-hour OGTT, HgbA1C, Vitamin B12, and serum immunofixation and serum pregnancy test (pregnancy test for women of child-bearing potential only). See section 7.1.12.
- Administer the *Utah Early Neuropathy Scale* (UENS). See section 7.1.10.
- Perform clinical assessment for suicidal ideation with the *Columbia-Suicide Severity Rating Scale* (C-SSRS). See section 7.1.15.

All clinical and laboratory evaluations, procedures related to inclusion/exclusion criteria, or assessments performed during treatment will be reviewed, initialed and dated by the Principal Investigator or the individual specifically designated by the investigator on the delegation of responsibility (DOR) log.

6.3. Re-screening

In the event a participant is originally found to be ineligible at the screening visit, but the investigator believes they may subsequently be eligible based on changes to the participant's circumstances or the study protocol, the participant may return for another screening visit (re-screening visit). If the original screening visit was conducted greater than 90 days before the re-screening visit, the re-screening visit will be treated the same as the original screening visit (see section 6.2).

- If the original screening visit was conducted **within 90 days** prior to the re-screening visit, the following data may be re-used from the original screening visit:
 - Serum immunofixation
 - Two-hour OGTT
 - Vitamin B12 results
 - Resting 12-Lead ECG
- If the original screening visit was conducted **within 30 days** prior to the re-screening visit, the following may be re-used from the original screening visit:
 - General medical and detailed neuromuscular physical examination results.
 - Vital sign measurements including blood pressure (systolic and diastolic), heart rate (beats/minute), and body temperature (°C).

- Weight (kg) and height (cm) measurements, and the calculated Body Mass Index (BMI).
 - Waist circumference (cm) measurement.
 - Blood sample results for CBC, fasting basic metabolic panel, fasting insulin, fasting lipid panel, two-hour OGTT, HgbA1C, Vitamin B12, and serum immunofixation and serum pregnancy test (pregnancy test for women of child-bearing potential only).
 - *Utah Early Neuropathy Scale (UENS)* results.
 - *Columbia-Suicide Severity Rating Scale (C-SSRS)* results.
- The following procedures **must be repeated** regardless of timeframe between the original screening visit and re-screening visit:
 - Review inclusion/exclusion criteria.
 - Detailed medical, family, and neurological history to assess for possible exclusionary conditions.
 - Review concomitant medications, including all nutritional, herbal and alternative therapies.
 - Informed Consent
 - If a participant being rescreened had NCS performed as part of a prior screening visit, these data may be used for baseline data (assuming the participant proceeds to randomization) if the baseline visit occurs within 90 days of the original NCS performance date.

All clinical and laboratory evaluations, procedures related to inclusion/exclusion criteria, or assessments performed during treatment will be reviewed, initialed and dated by the Principal Investigator or the individual specifically designated by the investigator on the delegation of responsibility (DOR) log.

